#### 9.4.2 Interim Analysis

Two interim analyses are planned. The first will occur once all subjects who are treated using STSF catheter with EPU have completed their 3 months follow-up. The second interim will occur when all subjects who are treated using STSF catheter with EPU have completed their 6 months follow-up. The planned interim analysis will be based on data collected only in subjects who are treated using STSF catheter with EPU. For the safety endpoint, among patients with more than 3 months of follow-up at the time of the interim analyses, any atrio-esophageal fistula and PV stenosis occurring post procedure will be deemed PAE.

At each interim analysis, the trial will declare early success if the predictive probability of success at the final analysis is greater than or equal to 99%. Early success will be declared at an interim if:

- 1. The safety objective has been met, and
- 2. The effectiveness endpoint has greater than or equal to 99% predictive probability of success.

The predictive probability is the probability of observing the success rate larger than 0.50 if the study continues to the end, given the observed data.

All of the subjects will be followed up to 12 months even after we claim success at interim look and submit the results in support of a premarket application. A final CSR will be submitted after all of the subjects complete their 12 months follow-up.

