### 9. STUDY MANAGEMENT

#### 9.1 Study Timelines

Study Duration: The study is expected to last Approximately 2.5 years (~1.0 years for enrollment; 12 months of follow-up for primary endpoint).

Expected date of study initiation	3Q 2018
Expected monthly number of study sites with IRB approvals	1 to 5 sites per month
Expected number of subjects enrolled per month	1.7 subjects per site/month; average 20 subjects per month over 12 months
Expected date of enrollment completion	3Q2019
Expected date of study follow-up completion	3Q2020
Expected date for Final Report submission	4Q2020

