#### 1. STUDY DESIGN

The SURPOINT COA study is a prospective, multicenter, non-randomized clinical evaluation of the VISITAG SURPOINT Module with EPU when used with the THERMOCOOL SMARTTOUCH® SF catheter (STSF) catheters or the THERMOCOOL SMARTTOUCH® (ST) catheter in treating subjects with symptomatic paroxysmal atrial fibrillation (PAF) who have failed at least one antiarrhythmia drug. A maximum of 330 subjects will be enrolled across up to 45 sites. Two hundred eighty (280) subjects will be treated using the STSF catheter with EPU and 50 subjects will be treated using the ST catheter with EPU. A few sites will be selected to enroll subjects to be treated only with the ST catheter. The remaining sites will enroll subjects to be treated with the STSF catheter. Two interim analyses are planned to take place after all subjects who are treated using the STSF catheter with EPU have completed their 3-month and 6-month follow-up visits for the evaluation of early success. The planned interim analysis will be based on data collected only in the subjects who are treated using STSF catheter with EPU. The final analysis of the primary effectiveness and safety endpoints will be based on all subjects's full 12-month follow-up data. Effectiveness and safety endpoints defined in association with the primary study objectives will be compared to the predetermined performance goals.

Enrolled subjects who satisfy all eligibility criteria will undergo the ablation procedure with the catheters and VISITAG SURPOINT Module. After the study ablation procedure, subjects will enter a 3-Month blanking period (Day 0-90). After the blanking period, subjects will enter the evaluation period (Days 91-365). Subjects having AF recurrence and/or receiving therapeutic interventions during the evaluation period will be considered effectiveness failures.

All subjects will undergo follow up visits at defined intervals (refer to Table 5-1 Schedule of Treatments and Evaluations in protocol). Subjects complete the SURPOINT COA study after the 12-month follow up visit.

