#### **5.1.2** Primary Safety Endpoint

The primary safety endpoint is the proportion of subjects with any primary adverse event (PAE) occurring within 7 days following an AF ablation procedure (including the initial and repeat procedures) using the STSF/ST catheter with EPU, except atrio-esophageal fistula and PV stenosis , which may also be considered as primary adverse events if occurring greater than 7 days post the ablation procedure. The PAE rate will be compared against the performance goal of 14%.

The final analyses for primary safety endpoint will apply Bayesian methods and use a beta-binomial model .

The hypotheses to be tested for this evaluation are:

$$H_0: q \ge 0.14$$
 vs.  $H_A: q < 0.14$ 

where q is the PAE rate.

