#### 9.4 Analysis of Primary Endpoints

The primary effictiveness endpoint is the proportion of patients that are free from primary effectiveness failure at Month 12. The failure modes are defined in the section 5.1.1. The effectiveness success rate at Month 12 will be compared against the performance goal of 50%. The final analyses will apply the Bayesian methods using a beta-binomial model. The analysis population for the primary effectiveness endpoint will be the per protocol (PP) population.

The primary safety endpoint is the proportion of patients that had Primary Adverse Event (PAE) within 7 days (PV stenosis and atrio-esophageal fistula may occur up to 3 months). The PAE rate will be compared against the performance goal of 14%. The final analyses will apply the Bayesian methods using a beta-binomial model. The analysis population for the primary safety endpoint will be the safety population.

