#### 9.4.1 Final Analysis

The primary goal of the trial is to demonstrate effectiveness and safety. For the trial to be successful, both endpoints must be statistically significant relative to their respective PG goals.

The effectiveness endpoint will be assessed by testing the hypotheses:

$$H_0$$
:  $Pr(p > 0.5|x, n) \le 0.97$  vs.  $H_A$ :  $Pr(p > 0.5|x, n) > 0.97$ 

where p is the responder rate, x is the observed number of patients that are failure-free through 12 months ("responders"), and n is the number of subjects in the PP population. If the posterior probability of the primary effectiveness endpoint meeting the 50% PG is greater than 97%, then we meet the threshold for primary effectiveness success.

We model the number of responders

$$X \sim \text{Binomial}(n, p)$$
,

We use a Beta (0.01, 0.01) prior distribution. This prior is centered at 50% and has an effective sample size of 0.02 observations.

Then the posterior distribution is

$$(p|x,n) \sim \text{Beta}(0.01 + x, 0.01 + n - x).$$

Subjects with missing data on the effectiveness endpoint will have their outcomes multiply imputed from a longitudinal model.

Similarly, the hypothesis test for the safety endpoint is:

$$H_0$$
:  $\Pr(q < 0.14|y, n) \le 0.95$  vs.  $H_A$ :  $\Pr(q < 0.14|y, n) > 0.95$ 

where *q* is the PAE rate, y is the observed number of subjects who had PAE and n is the number of subjects in the safety population. If the posterior probability of the primary safety endpoint meeting the 14% PG is greater than 95%, then we meet the threshold for primary safety success.

We model the number of patients with PAE as

$$Y \sim \text{Binomial}(n, q)$$

with Beta(1, 1) prior distribution on q. No imputation for missing data will be performed for the safety endpoint.

The trial will be considered a success if BOTH

- 1. Pr(p > 0.5|x, n) > 0.97 AND
- 2. Pr(q < 0.14|y, n) > 0.95.

These thresholds control the overall Type I error rate for the trial below one-sided 5%. The Type I error for each endpoint individually is also below 5%. The protocol Appendix B contains a detailed description of the statistical methods planned for testing the hypotheses around the primary effectiveness and safety endpoints.

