Note that the final analysis will be performed if early success is not declared at either of the two interim looks. If early success is declared at either of the two interim looks, a summary of the primary endpoints based on full 12-month follow-up will be provided. In addition, both safety

and effectiveness results will be descriptively summarized separately for patients treated with the ST and STSF catheters.

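### The interim can declare primary safety met before PAEs after later repeat ablations are in, and the plan does not say that the complete 12-month safety result then governs

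*SAP*

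**What the plan says.** **Endpoint.** SAP 5.1.2 counts a PAE "occurring within 7 days following an AF ablation procedure (including the initial and repeat procedures) using the STSF/ST catheter with EPU". Protocol 5.18 leaves repeat ablation to the physician's discretion and sets no end date. For the final look, SAP 1 states: "The final analysis of the primary effectiveness and safety endpoints will be based on all subjects's full 12-month follow-up data".

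**Interim rule.** The looks come when all STSF subjects have completed 3 and 6 months, and use STSF data only. The lead sentence of SAP 9.4.2 asks for at least 99% predictive probability of success at the final analysis, and SAP 9.4.1 defines trial success as both endpoints passing. The numbered conditions are narrower. For safety the condition is only "The safety objective has been met, and"; the 99% figure attaches to effectiveness alone, and predictive probability is then defined by the effectiveness rate exceeding 0.50. Protocol 7.9.4.2 reads the same way. SAP 9.4.1 adds: "No imputation for missing data will be performed for the safety endpoint".

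**Late events.** SAP 9.4.2 has one rule: fistula and PV stenosis count in patients with more than 3 months of follow-up. SAP 9.4 describes the endpoint as PAEs "within 7 days (PV stenosis and atrio-esophageal fistula may occur up to 3 months"), whereas SAP 5.1.2 puts no upper limit on those two events.

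**After early success.** The final analysis is not run; instead, "a summary of the primary endpoints based on full 12-month follow-up will be provided" (SAP 9.4.1).

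**The concern.** A subject whose repeat ablation falls after the data cut is scored at the interim as finally PAE-free. The number of subjects with a PAE can only stay the same or rise by Month 12, while the 14% goal and the 0.95 threshold do not move. The interim therefore applies the final criterion to a quantity that is never larger than the final one. The error has one direction, and it arises at a single look, apart from any cost of looking repeatedly.

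Two things are at stake. SAP 6 claims one-sided 5% control for interim and final analyses, and SAP 9.4.1 claims it for each endpoint individually. SAP 9.4.2 also foresees submitting an interim success in support of a premarket application, yet no rule covers the case where the complete safety data miss the criterion that the interim data met.

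**Working it through.** **1. The plan's own figure.** SAP 8 claims more than 90% power per endpoint at 65% effectiveness and 8% PAE, with 330 enrolled and 10-15% attrition. Safety passes when the Beta(1+y, 1+n−y) distribution function at 0.14 exceeds 0.95.

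| n | Max PAEs | Pass at 14% | Pass at 8% |
|---|---|---|---|
| 281 (330 × 0.85) | 29 | 4.1% | 93.4% |
| 297 (330 × 0.90) | 31 | 4.2% | 94.6% |

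The effectiveness bars are 157 and 165 responders, with power above 99.9%. The claim reproduces for a final analysis on complete data.

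**2. What is complete at interim 1.** Every followed STSF subject has passed the 7-day window, the 30-day tamponade window (Protocol 4.1.2) and the 3-month window of SAP 9.4 for the index procedure. Still pending are PAEs after later repeats and, if SAP 5.1.2's open-ended wording governs, late fistula or PV stenosis.

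**3. Share of repeats not yet seen.** Protocol 9.1 gives "1.0 years for enrollment; 12 months of follow-up for primary endpoint". Assume uniform accrual over 12 months and repeats uniform over months 3-12. Follow-up f is then uniform on (3, 15) months at interim 1 and (6, 18) at interim 2. The unseen share is u = E[max(0, 12−f)]/9.

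- Interim 1: (9²/2)/12/9 = 0.375
- Interim 2: (6²/2)/12/9 = 0.167

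**4. Pending events.** With 280 × 0.90 = 252 treated STSF subjects the bar is 26 PAEs (posterior 0.951 at 26, 0.928 at 27). Assume that a share r = 5%, 10% or 15% have an evaluation-period repeat with the study catheter and EPU, and that the PAE risk per repeat is 8%. Pending PAEs = 252 × u × r × 0.08.

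**5. Chance of passing at a true complete rate of 14%.** The rate visible at the interim is 0.14 − u × r × 0.08; the pass chance is the Binomial(252) probability of at most 26.

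| r | Pending, interim 1 | Pass, interim 1 | Pending, interim 2 | Pass, interim 2 |
|---|---|---|---|---|
| 0 | 0 | 5.1% | 0 | 5.1% |
| 5% | 0.38 | 5.9% | 0.17 | 5.4% |
| 10% | 0.76 | 6.7% | 0.34 | 5.8% |
| 15% | 1.13 | 7.6% | 0.50 | 6.1% |

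A simulation of 40,000 trials gave 5.7%, 6.8% and 7.5% at interim 1.

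**6. Sensitivity.**
- If only half the repeats use the EPU, interim 1 gives 5.5-6.3%.
- If the risk per repeat equals the risk per index procedure, with the total held at 14%, the visible rate is 0.14 − u × r × 0.14/(1+r). Interim 1 then gives 6.4%, 7.8% and 9.2%.
- Accrual of 330 at 20 per month takes 16.5 months, so u = (9²/2)/16.5/9 = 0.27 at interim 1 and pending events fall by about a quarter. A linear ramp over 12 months gives u = 0.56 and raises them by half.

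**7. Reversals at the planned 8% rate.** In the simulation, interim 1 passed safety but the complete STSF data missed the bar in 1.1%, 2.2% and 3.0% of trials for r = 5%, 10% and 15%.

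**The case against.** The strongest reply is that primary safety is in substance an acute endpoint, nearly complete at interim 1, and that about one event is pending against a bar of 26. That is right on size. The repeat rate, its timing and the risk per repeat are my assumptions, and only repeats with the study catheter and EPU count. The 5.1% baseline at n = 252 already exceeds 5% because counts are discrete; at n = 255, with the same bar, it is 4.4%. The pass chances also take the effectiveness condition as met.

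Three stronger readings are tempting, and the documents do not support them.

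- *Most safety data are missing.* Uniform 12-month accrual would leave 9/12 = 75% of STSF subjects short of 12 months at interim 1 and 6/12 = 50% at interim 2. A reader might take these as the size of the gap, but the index-procedure windows have closed. Nor are the percentages firm: Protocol 9.1's 20 per month for 12 months makes 240, not 330, and sites start in stages. Other readings of that table give 55-99% and 36-83%.
- *No test would notice a reversal.* SAP 9.4.4 schedules sensitivity analyses once all subjects complete or reach Month 12, and SAP 9.4.4.1 includes an exact binomial analysis of primary safety. A reversal would show there. What is missing is a statement that any such result governs.
- *There is no rule for late events.* SAP 9.4.2 has one for fistula and PV stenosis; the gap is repeat procedures. Both documents also refer to an appendix (B or C) that I have not seen and that may hold a rule.

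Finally, *through 12 months* is written out only for the secondary PAE rate (SAP 5.2.2). For the primary endpoint it follows from SAP 5.1.2 and SAP 1 read together.

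**Conclusion.** The concern holds as a modest, one-directional mismatch between the interim safety criterion and the endpoint it is meant to decide. As written in SAP 9.4.2 and Protocol 7.9.4.2, safety can be declared met while PAEs after later repeat ablations are outstanding, and the full-data result has no stated authority over that declaration. Under the assumptions in steps 3 and 4, the chance of passing safety at the 14% goal rises by about 1 to 2.5 percentage points at interim 1 and by at most 1 point at interim 2. It rises less if some repeats do not use the EPU, and more if accrual is back-loaded or repeats carry a higher risk. This does not undermine the design, but the plan should settle it. Two inconsistencies need reconciling whatever the size: the lead sentence of SAP 9.4.2 against its numbered conditions, and the open-ended window of SAP 5.1.2 against the 3-month limit in SAP 9.4.

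**What to change.** In SAP 9.4.1 and 9.4.2, and in Protocol 7.9.4.1 and 7.9.4.2, state that interim safety success is provisional. After early success, Pr(q<0.14|y,n)>0.95 is then applied to the complete 12-month STSF safety data, and that result governs the safety conclusion. Define the interim safety data cut, make the lead sentence of 9.4.2 agree with its numbered conditions, and use one window for fistula and PV stenosis throughout.

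Because the count can only rise, any trial that passes on complete data has also passed at the interim. For one look at n = 252, the chance of a governing safety success at 14% therefore returns to 5.1%.

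The cost is wording plus one calculation; all subjects are followed to Month 12 anyway. About 1-3% of interim safety declarations would be reversed at the planned 8% rate. Projecting safety at the interim with a 99% predictive probability is a stricter alternative. It lowers the bar by about 2-4 events and cuts the chance of clearing safety at interim 1, at 8%, from about 94-95% to 79-86%. That is a high price for a gap of this size, so I would not press for it.

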#### 6. LEVEL OF SIGNIFICANCE

The type I error for the interim and final analyses of the primary endpoints is controlled at one-sided 5%.

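### The interim early-success rule defines predictive probability by an observed rate above 0.50, not by the 0.97 posterior criterion that defines success at the final analysis

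*SAP*

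**What the plan says.** SAP 9.4.2 sets the interim trigger as follows: "the trial will declare early success if the predictive probability of success at the final analysis is greater than or equal to 99"%. It then restates this as two conditions, safety met and at least 99% predictive probability for effectiveness. A few lines later it defines the term: "The predictive probability is the probability of observing the success rate larger than 0.50 if the study continues to the end". Protocol 7.9.4.2 has the same rule and the same definition.

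Final success is defined differently in SAP 9.4.1 (Protocol 7.9.4.1 gives the same thresholds): "If the posterior probability of the primary effectiveness endpoint meeting the 50% PG is greater than 97"%, the effectiveness threshold is met. The prior is Beta(0.01, 0.01).

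Three other statements matter here.

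- After an early success the formal final test is not run. SAP 9.4.1 says instead that "a summary of the primary endpoints based on full 12-month follow-up will be provided". SAP 9.4.2 foresees submitting the interim results in support of a premarket application.
- SAP section 6 states: "The type I error for the interim and final analyses of the primary endpoints is controlled at one-sided 5"%. SAP 9.4.1 adds that each endpoint on its own also stays below 5%.
- The interims use STSF subjects only, whereas under SAP section 1 "The final analysis of the primary effectiveness and safety endpoints will be based on all subjects's full 12-month follow-up data".

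**The concern.** The 99% threshold is attached to two different events. One is meeting the final criterion, a posterior probability above 0.97. The other is finishing with more than half of subjects as responders, which is close to a coin toss when the true rate is 50%. Neither document says that the second is shorthand for the first.

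If the group running the interims programs the definition as written, an interim can declare success on data that point to a final result well short of the final criterion. The interim then becomes an easier test than the final one. Because an early declaration removes the formal final test, the 5% limit claimed for the interim and final analyses together would not hold for effectiveness.

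A second gap widens the uncertainty. The documents do not say whether the predicted final data set is the STSF subjects or all subjects.

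**Working it through.** **Inputs from the documents.** Performance goal 0.50, threshold 0.97, prior Beta(0.01, 0.01) (SAP 9.4.1); 280 STSF and 50 ST subjects, 10-15% attrition, planning rates 65% and 8% (SAP 8); looks when all STSF subjects reach 3 and 6 months, 99% threshold (SAP 9.4.2); piecewise exponential imputation over 39 post-blanking weeks with cuts at 2 and 8 weeks and Gamma(1,1) priors (SAP 9.4.3).

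**Step 1: the plan's own figures.** The posterior is Beta(0.01+x, 0.01+n-x). At n = 297 (330 less 10%) the smallest x with posterior probability above 0.97 is 165:

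- x = 164: Pr(p>0.5) = 0.964, fails.
- x = 165: Pr(p>0.5) = 0.973, passes; 165/297 = 55.6%.

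The single final test then has type I error P(X ≥ 165 | n = 297, p = 0.50) = 3.2% and power above 99.9% at p = 0.65. For safety at n = 297, at most 31 events are allowed, with type I error 4.2% and power 94.7% at 8%. So power above 90% and type I error below 5% reproduce for the final test.

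**Step 2: the two events side by side.**

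| n | Responders for posterior > 0.97 | Responders for rate > 0.50 | Posterior probability at the lower count |
|---|---|---|---|
| 252 (STSF only, 280 less 10%) | 141 (56.0%) | 127 | 0.55 |
| 297 (all, 330 less 10%) | 165 (55.6%) | 149 | 0.52 |

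The gap at n = 297 is 165 - 149 = 16 responders.

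**Step 3: type I error over both interims and the final analysis.** The design was simulated at p = 0.50 with 6,000 trials per scenario. Assumptions that the documents do not give:

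- 252 STSF and 45 ST subjects, with no loss to follow-up.
- Uniform accrual over 52 weeks or 71.5 weeks. Protocol 9.1 says "average 20 subjects per month over 12 months", but 330/20 = 16.5 months, so both durations were run.
- Looks 13 and 26 weeks after the last STSF subject is treated.
- Share of cumulative hazard in the three segments: constant 5/15/80%, front-loaded 20/25/55%, strongly front-loaded 35/30/35%.
- Safety condition taken as met; final test x ≥ 165 of 297.

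| Accrual | Hazard | Written definition, all subjects predicted | Written definition, STSF only predicted |
|---|---|---|---|
| 52 weeks | constant | 10.0% | 14.2% |
| 52 weeks | front-loaded | 11.0% | 16.1% |
| 52 weeks | strongly front-loaded | 13.3% | 20.2% |
| 71.5 weeks | constant | 10.9% | 16.7% |
| 71.5 weeks | front-loaded | 13.1% | 20.6% |
| 71.5 weeks | strongly front-loaded | 14.3% | 23.4% |

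When the 0.97 criterion is predicted instead, the result is 2.9-3.5% in every scenario. The Monte Carlo standard error is about 0.4-0.5 points for the written definition. Under that definition, 72-86% of the early successes at p = 0.50 would end below 165 of 297.

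**Step 4: checks.** A separately written simulation (250 STSF and 50 ST, STSF-only prediction, 52-week accrual, 8,000 trials per shape) gave 13.5% with constant hazard and 15.9% with hazards in ratio 6:3:1, against 2.8% and 2.9% for the 0.97 criterion. Stress runs with accrual of 6 to 24 months and a back-loaded hazard gave 6.4-27.5% against 2.7-3.6%.

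**Step 5: the safety condition.** With 252 STSF subjects, safety is met with at most 26 events (posterior probability 0.951). At a true rate of 8% that happens 92.5% of the time. Multiplying gives roughly 10.0% × 0.925 = 9.3% to 23.4% × 0.925 = 21.6%, still above 5%.

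**The case against.** The strongest reply is that this is loose wording. The operative rule, stated twice in the same section, refers to success at the final analysis, and success has just been defined by the 0.97 criterion. The disputed sentence can be read as an informal gloss for beating the 50% goal, echoing the alternative hypothesis p > 0.50. Only that reading fits the stated 5%. Both documents also send the detailed methods and simulations to a protocol appendix (C in the Protocol, B in the SAP) that is not part of the reviewed text and may state the rule correctly.

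Much of this stands. The 0.97 reading is probably the intended one, the inflated error rates apply only if the sentence is implemented literally, and their size depends on accrual and hazard assumptions. The practical stakes are also smaller if the true rate is near 65%. Every subject is followed to 12 months, and the final report and sensitivity analyses would expose a marginal early success.

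It does not repair the text. The sentence speaks of observing a rate, it is the only definition given, and it can be programmed as it stands. An independent group runs the interims, the sponsor is not blinded and there is no data monitoring committee, so the written rule should have one meaning. Later exposure of a weak result does not restore error control once success has been declared. If the appendix uses the 0.97 criterion, the SAP and Protocol contradict it; if it uses the written event, the 5% claim is in doubt. Either way the sentence has to change.

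**Conclusion.** The concern holds. As written, the interim rule names one event and defines another, and the defined one is materially weaker. Read literally, it raises the effectiveness type I error from about 3% to 10-23% across the planned-accrual scenarios, against a stated limit of 5%. Which subjects are predicted accounts for a good part of that range. Even the lowest stress-run figure, 6.4%, exceeds the limit.

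Confidence is high that the text conflicts and that the literal rule cannot meet the 5%. Whether the design as actually simulated has this fault cannot be judged without the appendix. The sizes rest on the accrual, hazard, attrition and follow-up assumptions listed above, which change the amount of inflation but not its direction.

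**What to change.** In SAP 9.4.2 and Protocol 7.9.4.2, replace the definition with: *The predictive probability is the probability, given the interim data, that the final analysis will satisfy Pr(p>0.5|x,n) > 0.97 at the final sample size.* State whether the predicted final set is the STSF subjects alone or also includes the ST subjects, and if so how their outcomes are predicted from STSF data. Confirm that the appendix simulations behind the 5% claim used this rule and this set; if they did not, rerun them.

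The cost is one sentence per document, one clarification and a check of the simulation report. Early success becomes less likely than under the literal rule. At p = 0.65 the effectiveness condition is met by the first interim in 74-93% of simulated trials instead of 98-100%, and by the second in 94-99% instead of about 100%. Effectiveness power by the final analysis stays at about 100%.
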